## **5. TIME LINE**

Phases of project development, with activities and tasks to be developed by the entire research team:

### **Preparation phase**

- Activity 1-** Registration and publication of study protocol
- Activity 2-** Design of questionnaires and nutrition education material
- Activity 3-** Design and development of the nutritional blog
- Activity 4-** Presentation of the project to PCCs
- Activity 5-** Training of Associate Researchers (PCC health professionals)

### **Implementation and follow-up phase**

- Activity 7-** Recruitment of patients. Beginning of the intervention
- Activity 8-** Data collection, introduction to DCQ
- Activity 9-** Conduct follow-up visits (in person and by telephone)

### **Data analysis and final evaluation**

- Activity 10-** Periodic quality analysis of records
- Activity 11-** Statistical analysis. Communication and publication of intermediate results
- Activity 12-** Statistical analysis. Communication and publication of final results

The schedule of tasks and data collection at each visit during the implementation and follow-up phase is detailed below.

	Visit 0	Visit 1	Visit 2	Visit 3	Visit 4	Visit 5
Study timeline	- 30 days	Day 0	6 months	12 months	18 months	24 months
Aims	Randomization Selection Inclusion	Data collection Intervention	Phone follow-up Reinforcement	Data collection Intervention	Phone follow-up Reinforcement	Data collection Reinforcement
Procedures						
Informed consent	X					
Online data collection (DCQ)	X	X	X	X	X	X
Basic physical examination		X		X		X
Laboratory tests	X					
Food questionnaires and dietary information		X		X		X
Forced spirometry	X			X		X
Inflammation / oxidation markers		X		X		X
Intervention						
Control group: usual diet, usual clinical consultations, telephone follow-up		X	X	X	X	
Intervention Group: MD Nutrition Program		X	X	X	X	

## 6. LIMITATIONS AND STRENGTHS OF THE STUDY

The present study has several limitations. The most important is related to the study population, because inclusion criteria may limit successful recruitment.

The intervention may be less intensive than that described in cardiovascular prevention studies [28]. However, it is an innovative strategy in the prevention of respiratory pathology and its pragmatic design take into account the actual working conditions in daily clinical practice in primary health care. It focuses on reinforcing the consumption of foods considered as protective in the typical diet of the Mediterranean region and reducing the consumption of foods in the standard Western diet that have harmful effects on pulmonary physiology. If the efficacy of this intervention can be demonstrated, it could be readily implemented in clinical practice.

Another limitation to take into account is the knowledge about dietetics and nutrition and the skills of the collaborating health professionals. Knowledge and skills are essential to properly evaluate MD adherence in terms of specific foods, as well as to increase the validity and reliability of the information collected using the study questionnaires and nutritional education. Therefore, in order to standardize the intervention, the dieticians who collaborate in the MEDISTAR study and who design the intervention and develop the educational content and materials will provide thorough training in MD and pulmonary function at the beginning of the study for all participating health professionals.

The effect on lung function will be evaluated by comparing the results of three consecutive forced spirometry measurements, taken annually during the three-year project period. Although this should be sufficient time to allow observations about the longitudinal effect of the diet on spirometry values, it could be too short to show statistically and clinically significant differences between the two study groups. In any case, these results should provide additional evidence of the effect of a MD on lung function in a population of smokers with no previous respiratory disease.

A common limitation of long-term projects is the loss of participants during the follow-up. To minimize losses, a multicomponent intervention involving technology has been designed. The use of a nutritional blog is intended to facilitate interaction between participants in the intervention group and the researchers, beyond the scope of the office visit, and should favor adherence during the study period. Moreover, annual telephone contacts should help to consolidate the intervention and maintain direct personal contact with all participants in both study groups.

The MEDISTAR study also has important strengths. It takes a multidisciplinary approach to the serious health problem caused by tobacco use, integrating elements of epidemiological, clinical, and basic research. In addition, the research team includes professionals with complementary experience in conducting clinical trials of lifestyle interventions. The intervention is carefully structured to determine its effect on the main clinical outcomes and maximize its transferability to the primary health care setting.

This highly innovative project offers a new paradigm of nutritional recommendations to address pulmonary dysfunction in smokers. This approach, drawing on a field of nutrition that has scarcely been studied and online new technology that is already familiar to much of the study population, may contribute to better adherence to the intervention.

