#### **4.4. INTERVENTIONS**

Participating centers will be assigned randomly to a control or intervention group (1:1). Volunteers will be referred to an initial visit (V0) to confirm inclusion criteria and sign an informed consent (Annex 1). Basal variables will be collected at that time.

Participants from the intervention PCCs will enter into an educational program to increase adherence to the MD. It will consist of five contacts that integrate three operational components:

- a) Explain the details of the MD and the benefits of following this dietary pattern in an individual visit of 25-30 minutes (V1). Data on the study variables will be collected and medical tests will be performed. This data gathering will be repeated annually for two years (V3 and V5).
- b) Clarify any doubts about following the MD pattern and other advice received, in a telephone conversation. This annual contact will reinforce the intervention (V2 and V4).
- c) Provide information about MD foods, cooking tips, adapted recipes, and other related topics in an ad hoc nutrition blog.

The control group will carry out the same 5 visits (3 individual visits and 2 phone calls), although no changes will be made in their usual diet and they will not be provided with access to the nutritional blog.

All participants will receive health advice to stop smoking, according to the protocol recommended to health professionals in Catalonia: a proposal of smoking cessation expressed in a clear, firm, and personalized way, in an empathic and respectful setting.

At the end of the study, if the intervention is effective, control group members will be invited to participate in the same intervention program.

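### Mediterranean-diet training is planned for all participating health professionals, with no split by arm, which exposes the control centres to contamination

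*Combined protocol and SAP*

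**What the plan says.** Section 6 (Limitations and strengths) names the dietetic knowledge of the collaborating professionals as a limitation. Its remedy is that "in order to standardize the intervention, the dieticians who collaborate in the MEDISTAR study and who design the intervention" and write its educational content "will provide thorough training in MD and pulmonary function at the beginning of the study for all participating health professionals". The same paragraph gives a second reason for staff knowledge: "Knowledge and skills are essential to properly evaluate MD adherence in terms of specific foods".

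Section 5 lists one training item in the preparation phase, Activity 5, for the health professionals of the primary care centres. It precedes recruitment (Activity 7) and is not divided by arm.

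Section 4.4 uses the word participating for both arms: "Participating centers will be assigned randomly to a control or intervention group (1:1". Control participants have three individual visits and two telephone calls, as in the intervention arm, "although no changes will be made in their usual diet and they will not be provided with access to the nutritional blog". The schedule table in section 5 describes their care as "Control group: usual diet, usual clinical consultations, telephone follow-up".

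The documents contain no arm-specific training, no script for control visits, no instruction to control staff about diet advice and no named contamination check. Section 6 does not list contamination among the limitations.

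**The concern.** A main benefit of randomising centres rather than patients is that different staff see the two arms. The plan pays for this with a design effect of 1.7. If the dietitians who wrote the intervention teach its content in the control centres too, part of that benefit is lost.

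The natural reading is that the trained professionals of each centre hold its study contacts and its usual consultations. Control staff would then know the tested diet and why it is thought to protect the lung before their first control visit. Some of that could reach control smokers without anyone departing from the protocol.

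The likely direction is a smaller difference between arms, both in lung function and in diet adherence (secondary objective 1). Section 6 already concedes that follow-up may be too short to show a difference. Contamination would add a second explanation for a null result. Training cannot be withdrawn once given, and no analysis restores an unexposed control arm.

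**Working it through.** **Who is trained, and when.** Four statements fit together:

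1. Section 6: diet training is for all participating professionals, at the start of the study.
2. Section 4.4: control centres are participating centres.
3. Section 5: training (Activity 5) precedes recruitment (Activity 7).
4. Section 4.4: controls then have 3 visits + 2 calls = 5 contacts.

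Nothing elsewhere restricts the diet content to one arm. A centre that follows the text would train control staff.

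**The plan's own sample size (section 4.3).** Inputs: 0.17 v 0.31, two-sided alpha 0.05, beta 0.2, 25% loss, arcsine method.

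- h = 2·asin(√0.31) − 2·asin(√0.17) = 1.1810 − 0.8500 = 0.3310
- n = 2·((1.960 + 0.842)/h)² = 143.3, rounded up to 144
- 144/0.75 = 192 per group, which matches the plan.

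Applying the design effect gives 192 × 1.7 = 326.4, so 327 per group or 654 in total. The stated 750 is larger. That is a separate matter, but it explains why the starting power below exceeds 80%.

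**Illustration of a leak.** Two assumptions are not in the documents. First, 0.31 is the control rate; section 4.3 says only group 1 and group 2. Second, controls obtain a share f of the 0.14 difference, with f between 0 and 30%.

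- Effective n per arm = 375 × 0.75/1.7 = 165.4
- Control rate = 0.31 − 0.14f
- Power = Φ(h·√(165.4/2) − 1.960), with h recomputed for each control rate

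| f | Control rate | h | Power |
|---|---|---|---|
| 0 | 0.310 | 0.331 | 85% |
| 10% | 0.296 | 0.301 | 78% |
| 20% | 0.282 | 0.270 | 69% |
| 30% | 0.268 | 0.238 | 58% |

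**Sensitivity to the design effect.** About 375 × 0.75/10 = 28.1 participants per centre would be analysed. An intracluster correlation of 0.02 gives a design effect of 1 + 27.1 × 0.02 = 1.54, and power at a 10% leak is 82%. A correlation of 0.05 gives 1 + 27.1 × 0.05 = 2.36, and power is already 72% with no leak.

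**The case against.** The case on the other side has real force.

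- **A risk is not an event.** A reader might infer that the training contaminates the control arm, or that control staff are to teach the diet. The documents do not say so. Controls are to keep their usual diet, and section 6 gives no syllabus. This stands, and the point is limited to exposure.
- **The whole defined programme is withheld from controls.** A reader might think that controls miss only the education session and the blog. Section 4.4 has a third component, telephone reinforcement. Controls receive calls, but the plan assigns them no diet programme.
- **The wording could be narrower than it looks.** A purpose of standardising the intervention might mean only the staff who deliver it, and Activity 5 is one line in a task list. That is possible, but the word all, together with section 4.4, points the other way. If the narrower meaning was intended, the text still needs to say so.
- **Control staff need some training.** Adherence is scored in both arms. Training only one arm in assessment could make scoring of the 14-item questionnaire differ by arm. This stands and shapes the fix.
- **Drift in controls would be visible.** The plan collects adherence, food frequency and urinary polyphenols, and section 4.7 compares V1 with V5. It is therefore too strong to say that a null result could not be interpreted. Seeing drift, however, neither prevents it nor restores power, and no check is named.
- **The bias is conservative.** Dilution would not create a false benefit. That is true, but it could hide a real one.

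**Conclusion.** The point holds as an avoidable exposure. As written, the plan gives control-centre staff training in the tested diet before they meet control participants, with likely bias toward zero in adherence and lung function.

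Its size cannot be derived from the documents. The fall in power from 85% to between 78% and 58% rests on an assumed leak of 10% to 30%, on 0.31 being the control rate, and on the design effect of 1.7. It shows how sensitive the trial is to a leak and is no evidence that the training causes one.

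Nor should a reader conclude that a 10% leak is a threshold at which the planned power fails. The shortfall there is 78% against 80%, and it disappears with a design effect of 1.54. The case for change is that the exposure is cheap to remove beforehand and cannot be undone afterwards.

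**What to change.** Revise the training paragraph in section 6 and Activity 5 in section 5 as follows:

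1. **Common module, all centres:** spirometry, identical and neutral administration and scoring of the food-frequency and 14-item questionnaires, sample collection, and the smoking-cessation advice already planned.
2. **Diet education module, intervention-centre staff only:** counselling content and educational materials. Offer it to control-centre staff after the last V5; section 4.4 already foresees inviting controls into the programme at the end of the study if it proves effective.
3. **Order of events:** state that centres are allocated before the second module is given, and reconcile this with the schedule table, which lists randomisation at Visit 0.
4. **Contamination check:** in section 4.7, prespecify reporting of the V1 to V5 change in diet adherence and urinary polyphenols in the control arm. Section 4.5 already lists both measures. The schedule table has no row naming polyphenols, so confirm that they are taken at V1 and V5. A rise in controls may have other causes, so the check describes drift and does not attribute it to training.

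The cost is two training sessions instead of one, earlier allocation of centres, and care to keep questionnaire scoring the same in both arms. It needs no additional participants, staff or measurements.

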## **7. ETHICAL ASPECTS**

The study will follow the principles set out in the Declaration of Helsinki and the guidelines of Good Clinical Practice of the International Conference on Harmonization (ICH GCP). It also fulfills the requirements established in the legislative framework in Spain for the field of biomedical research, the protection of personal data and bioethics, as well as the published guidelines of good clinical practice.

The protocol has been evaluated by the Ethics Committee of IDIAP - Jordi Gol, incorporating its recommendations and suggestions.

During recruitment, all individuals will receive information about the study objectives and the activities related to their participation, and will sign an informed consent prior to their inclusion (Annex 1).

## **8. AVAILABLE INSTRUMENTATION AND FACILITIES**

The research team has the institutional support of the ICS Directorate of Primary Care for Tarragona Province. During the project period, researchers will have the use of facilities belonging to ICS primary care centers in the cities of Tarragona and Reus and will have the technical resources at their disposal need for the study, including the blog and follow-up telephone calls. All the centers participating in the study function as primary care teams, with a common electronic medical registry system (e-CAP) managed by ICS. All PCCs have the physical space necessary for the laboratory tests to be carried out, in a confidential environment for the patients.

This project will also count on the collaboration of staff assigned to the Research Support Unit of the ICS Primary Care Area of Tarragona-Reus, which has the computing resources required to manage the data generated by the study. The economic and administrative management of the project will rely on the infrastructure of IDIAP - Jordi Gol, which includes the Study Group on Pathology of the Respiratory System. In addition, the Primary Care Area of Tarragona-Reus, through its research coordinator, is a member of the board of the Pere Virgili University Institute Board (Rovira i Virgili University, Tarragona), which provides access to the methodological and technical resources of these institutions.

## **9. FUNDING SOURCES**

This project fits within the Strategic Plan for Research and Innovation in Health (Catalan acronym, PERIS) for 2017-2019, with funding granted by the Department of Health of the Government of Catalonia.

## **11. ANNEXES AND FIGURES**

**Figure 1. Project flowchart: participant selection, randomization and follow-up.**
